# 4.2. Intervention.

All procedures will be conducted as part of standard of care. In the Pharmacist Care group, each e-visit message requesting Paxlovid will be assigned to a pharmacist on the regional team. Pharmacists will review requests using a standard protocol. They will call patients via telephone to elicit additional information where needed, file Paxlovid prescriptions when appropriate, and arrange home delivery when requested.

The protocol for pharmacists has a list of common potential drug-drug interactions and provides guidance for how these should be handled. Drug-drug interactions are documented by pharmacists using a smartphrase in Epic, the electronic health record (EHR). Some DDIs may lead to changes in medications while a patient is taking Paxlovid.

In the AFM Pool Care group, each e-visit message requesting Paxlovid will be assigned to a pool of AFM physicians based at the medical centers in a given service area. Physicians will review requests using the existing standard regional protocol (as well as any existing medical center-level protocols). The regional Paxlovid E-visit User Guide illustrates how to use SmartSets to document the plan and respond to patients with the outcome (eligible, not eligible, or further discussion needed). Following this protocol, physicians call patients via telephone to elicit additional information where needed, file Paxlovid prescriptions when appropriate, and arrange home delivery when requested.

4.3. Randomization. In each of the participating service areas, facilities have been assigned at random to either the Pharmacist Care or AFM Pool Care group. We used covariate-constrained randomization, a method to prevent imbalances on important variables that may be associated with the outcomes. We conducted preliminary analyses to characterize facilities with regard to population size, socioeconomic status (using the Neighborhood Deprivation Index), race, ethnicity, and COVID-19 incidence in the service area since the start of the pandemic. We have chosen these variables for use in the restricted randomization given the expected association with study outcomes, along with the expected level of between facility variability which would increase the likelihood of between-arm imbalance. We also stratify randomization on service area for within-area balance on number of facilities assigned to the Pharmacist Care and AFM Care groups.

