Using these variables, we enumerated all possible outcomes of randomization and eliminated all allocations of the facilities to the two groups that do not meet specified between-group balance criteria. Standard diagnostics were applied in selecting the covariate balance criteria, ensuring no threats to the validity of the study design, including extreme reductions in total possible allocations for the trial, and instances of cluster pairs never/rarely or always/often randomized to the same arm. An allocation of facilities to the two arms for implementation was randomly selected from the set of allocations that meet the final covariate balance criteria.

The balance criteria were: maximum 5% between arm difference in total membership, 30% difference in total Black, 20% for each of White, Asian and Hispanic race/ethnic groups, 25% difference in mean NDI, and 15% difference in mean COVID-19 incidence. We are applying no between arm balance criteria within strata/service area.

The selected randomization scheme leads to good balance between the intervention and comparison groups, with 4.8% difference in total membership (~565K vs ~513K), 11.7% for Black (23K vs 29K), 2.2% for White (183K vs 175K), 8.7% Asian (150K vs 126K), 7.8% Hispanic (127K vs 109K), 12.2% difference in mean NDI (-.49 vs - .44), and 2.7% difference in mean COVID-19 incidence (.23 vs .22).

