For the exploratory outcomes, patient care experience will be evaluated by surveying a sample of patients selected at random in the service areas in the Pharmacist Care and AFM Pool Care groups. We have designed a short survey that takes no more than 5 to 10 minutes to complete. The survey will be fielded by email, mail, and telephone. Due to the fact that we are asking about a specific care experience and patients' recall fades quickly after 2 weeks, we will field the survey using all 3 modes in a relatively efficient sequence. A letter containing a description of the study, language regarding informed consent and confidentiality, and the survey will be sent by mail on day 11 after the e-visit, and an email with a link to the online version will be sent on day 14. Telephone administration will be attempted (up to 4 attempts total) starting on day 17 for those who have not replied to the paper or online survey. A small gift to thank patients for considering participation will be included in the mailing. Responses will be treated as confidential and data will be aggregated, with no individual identifiers associated with data presented in reports.

Patient-reported outcomes will be reported on a 5-point scale and will include:

- a. Satisfaction with the overall quality of care
- b. Satisfaction with the timeliness of care
- c. Confidence in the care provided

Clinician satisfaction with the process of care will be evaluated by surveying all pharmacists on the regional team providing Pharmacist Care, plus the AFM site leads for Paxlovid e-visits in the service areas participating in the study. Because the AFMs in each service area cross-cover the Paxlovid e-visit requests from all facilities in that service area, it will not be possible to survey front-line AFMs in the two groups separately, and it would not be productive to ask the AFMs about their experience with Pharmacist Care because they would typically only have direct experience with Pharmacist Care if a problem arose that required their attention.

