A secondary analysis will treat each patient as part of the group to which they were assigned based on the facility listed on the e-visit worklist (intention-to-treat). However, this approach may be worse at reflecting the actual patient experience because dozens of pharmacists and physicians were involved in executing the randomization assignments. It is possible that some patients will have received a different mode of care from the group to which they were assigned.

The primary outcome is binary, i.e., whether or not a patient received counseling for a DDI. This will be compared between study groups using mixed effects logistic regression providing point and interval estimates of outcome odds ratios associated with study group. This analysis technique accounts for the within-facility correlation among patients to obtain valid estimates of treatment effects and associated standard errors. The pre-specified set of covariates for inclusion in regression models include: study group and covariates used in the randomization procedure (i.e. patient socioeconomic status (using the Neighborhood Deprivation Index), patient race/ethnicity, and service area level COVID-19 incidence). Study group and other covariates will be treated as fixed effects and the patient's home facility and e-visit facility will be handled as random effects.

In addition, exploratory/sensitivity analyses will examine the impact of including additional covariates in our estimation of treatment effect, with focus on variables with chance imbalance in distributions by treatment group, as determined in preliminary analyses. Analyses resulting in an appreciable change in the estimate of treatment differences or increased precision of the treatment effect will be noted.

For the secondary outcomes, we will compare the estimated cost per Paxlovid message, the minutes spent per message, and the hours from e-visit to prescription order between the Pharmacist Care and AFM Pool Care groups using linear mixed regression models, providing point and interval estimates of between-group differences in mean outcomes. If cost or minutes have a skewed distribution, log transformation will be used. Analyses of other secondary outcomes with that are continuous will be similar. The approach to inclusion of covariates and sensitivity/exploratory analyses is as described for Aim 1.

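### The model's list of randomisation covariates leaves out the stratum (service area) and total membership, so the intention-to-treat analysis adjusts for the design only in part

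*Combined protocol and SAP*

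**What the plan says.** Section 4.3 sets out the design. On the choice of variables: "We conducted preliminary analyses to characterize facilities with regard to population size, socioeconomic status", followed by race, ethnicity and area COVID-19 incidence. The reason given is: "We have chosen these variables for use in the restricted randomization given the expected association with study outcomes". On strata: "We also stratify randomization on service area for within-area balance on number of facilities assigned". Among the balance criteria, the tightest is "maximum 5% between arm difference in total membership", and the chosen allocation has "4.8% difference in total membership (~565K vs ~513K"). The section adds: "We are applying no between arm balance criteria within strata/service area".

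Section 4.6 then fixes the model terms as study group plus the "covariates used in the randomization procedure (i.e. patient socioeconomic status (using the Neighborhood Deprivation Index), patient race/ethnicity, and service area level COVID-19 incidence"), with home facility and e-visit facility as random effects. The Aim 2 models take over the same approach to covariates. The analysis by worklist facility, labelled intention-to-treat, is secondary; the primary analysis groups patients by the type of clinician who first opened the e-visit.

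**The concern.** The list in Section 4.6 is introduced by i.e., so it reads as complete, yet it does not match Section 4.3. It omits the stratification factor and one constrained variable. Section 4.4.2 (Predictors and covariates) does not supply them either.

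An analysis that keeps the randomised comparison would normally condition on the strata within which units were randomised. Stratifying removes between-area variation from the true error of the treatment contrast. A model without area leaves much of that variation in the estimated error, so the test is conservative and the interval too wide whenever areas differ. That is plausible here: Section 4.5 (Data collection) notes that "the AFMs in each service area cross-cover the Paxlovid e-visit requests from all facilities in that service area", and Section 4.2 (Intervention) allows local protocols at medical centers. What is at stake is some precision, and a model statement that contradicts the design it claims to follow.

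**Working it through.** **The plan's own figures.** The membership difference reproduces as (565 − 513)/(565 + 513) = 52/1078 = 4.8%, just inside the 5% limit, so membership was an operative constraint. The 250 per group also reproduces approximately. For 70% vs 56%, 186 per arm (200 with continuity correction) times a design effect of 1 + (29.4 − 1) × .01 = 1.284 gives 239 (257). Nothing below changes that number.

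**Side by side.** Used in the randomisation: service area, membership, race/ethnicity, Neighborhood Deprivation Index, area incidence. In the model: the last three. One incidence value per area can take up at most 1 of the 3 degrees of freedom among four areas.

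**Inputs.** From the documents: 17 facilities, 4 areas, ICC .01, 500 charts (m = 500/17 = 29.4 per facility), 1,560 e-visits for Aim 2 (m = 1560/17 = 91.8). Assumed: 4/4/4/5 facilities per area, incidence unrelated to area effects, a share s of facility variance lying between areas, equal clusters, a linear analysis of facility means, and a t reference.

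**Degrees of freedom.** Planned: 17 − 3 (intercept, group, incidence) = 14, t = 2.145. With area: 17 − 5 = 12, t = 2.179.

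**Width.** The total variance of a facility mean is .01 + .99/m = .0437 (chart) or .0208 (Aim 2). The within-area part is W = total − .01s. The planned residual variance is about P = W + (2/3)(12.71)(.01s)/14, where 12.71 = 17 − (16 + 16 + 16 + 25)/17 and the 2/3 reflects the degree of freedom taken by incidence. The ratio of planned to area-adjusted width is √(P/W) × 2.145/2.179. The simulated column comes from 30,000 replicates per setting, stratified by area and constrained on membership (coefficient of variation 0.5, assumed).

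| Outcome | s | W | P | Formula | Simulated |
|---|---|---|---|---|---|
| Chart | 0 | .0437 | .0437 | .984 | .985 |
| Chart | .25 | .0412 | .0427 | 1.002 | 1.003 |
| Chart | .50 | .0387 | .0417 | 1.022 | 1.022 |
| Chart | .75 | .0362 | .0407 | 1.044 | 1.044 |
| Aim 2 | 0 | .0208 | .0208 | .984 | .984 |
| Aim 2 | .25 | .0183 | .0198 | 1.024 | 1.023 |
| Aim 2 | .50 | .0158 | .0188 | 1.075 | 1.073 |
| Aim 2 | .75 | .0133 | .0178 | 1.140 | 1.134 |

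(Ratios were computed before rounding W and P.)

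**Type I error of the planned model** at s = .25/.50/.75, simulated with a t reference: 4.8/4.3/3.8% (chart) and 4.4/3.7/3.1% (Aim 2). With service area in the model it returns to about 5%.

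**Reference distribution.** Section 4.6 names none. Using 1.96 on a 12-df error estimate gives P(|t₁₂| > 1.96) = 7.4%; on the planned 14 df it gives 7.0%. Adding area terms without a small-sample reference would therefore be anti-conservative.

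**Membership.** Adding it to the area terms, when it is not prognostic, moves the s = 0 chart ratio from .985 to .963, a cost of .985/.963 = 1.023, or about 2% in width.

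**The case against.** The strongest reply is that the gain is small, conditional, and in a secondary analysis. Much of this stands.

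- For the chart outcome, the width gain from area adjustment is 0 to 4% over the assumed shares. If areas do not differ, there is a loss.
- Cross-cover by area is a mechanism for the AFM arm; pharmacists are one regional team with one protocol. With area differences in the AFM arm only, and both area and membership in the model, the simulated ratios are .969 to .982 (chart) and .977 to 1.008 (Aim 2). Removing the membership cost (× 1.023) leaves about −1 to 0% and 0 to +3%.
- Incidence was chosen because it may be prognostic. If it explains half of the area variance at s = .50 (assumption), the ratios with both terms added fall to .984 and 1.009.
- The calculations use facility means and a t test, whereas the plan specifies mixed models with two facility random effects. With a maximum-likelihood z test, simulated type I error was 4.7 to 9.0% for the planned terms and 5.5 to 11.8% with area and membership added. This is why the fix must name the reference distribution.
- Section 4.6 already allows sensitivity models with further covariates, but it names neither omitted variable and looks to chance imbalance found later.

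A reader might infer a large power loss. A simulation with area SDs of 0.4 to 0.6 on the log-odds scale does put power as low as 38%, against about 74% with area terms. Such SDs imply a total ICC of (.16 + .033)/(3.29 + .193) = .055 up to (.36 + .033)/(3.29 + .393) = .107, far above the planned .01, so the documents do not support that size of loss.

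**Conclusion.** The mismatch between Sections 4.3 and 4.6 is textual and needs no assumption. Its effect is incomplete adjustment for the design: a mildly conservative worklist-assignment test, with the same effect in the Aim 2 models under that grouping. Intervals are up to about 4% (chart) or 13% (Aim 2) wider than with area adjustment. These sizes rest on ICC .01, area shares of 25 to 75%, area differences present in both arms, incidence unrelated to those differences, and a t reference.

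Three stronger readings are tempting and do not hold:

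- That the analysis ignores the randomisation. It does not: the e-visit facility is a random effect, and three of the design variables are kept.
- That the intention-to-treat estimate is biased. Allocation was stratified, so the omission affects precision and error rate only.
- That the as-treated primary estimate is compromised, by this omission or because home facility enters only as a random intercept. That would need a link between area or home-facility effects and the share of patients seen by pharmacists, which the documents do not report.

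**What to change.** In Section 4.6, for the worklist-assignment analysis and the Aim 2 models under that grouping:

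1. Replace service-area COVID-19 incidence with a 4-level fixed effect for the service area of the e-visit facility. Incidence is constant within area, so the area terms absorb it; say so.
2. State a small-sample reference based on facility-level degrees of freedom (t with about 12).
3. Correct the list of randomisation covariates so that it agrees with Section 4.3.
4. Add facility membership only as a named sensitivity analysis. It costs about 2% in width if it is not prognostic, and the documents give no evidence of how prognostic it is.

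The cost is wording and a few model terms; both variables were already held for the randomisation. Two facility-level degrees of freedom are lost (14 to 12). If areas do not differ, the interval is about 1.5% wider (2.179/2.145 = 1.016) and chart-outcome power falls by about 1 point (76.6% to 75.4%, simulated).

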# 4. Approach

## 4.1. Design, setting, and participants.

This cluster randomized clinical trial will assign patient requests for Paxlovid made via e-visits to either Pharmacist Care or AFM Pool Care, which consists of management by medical centerbased pools of AFMs in adult and family medicine (AFM). The unit of randomization is the KPNC facility. KPNC is an integrated health care system with 4.6 million members served by more than 9,500 physicians and 87,000 employees in 15 service areas. It has a mature EHR (EPIC/HealthConnect, adopted circa 2008) and encourages members to use a wide array of options for outpatient care, including secure messages to physicians via the EHR portal, e-visits, video, telephone, and in-person office visits.

The target population is adults 18 years and older in facilities within participating KPNC service areas who submit requests for Paxlovid on weekdays during the study period using the e-visit protocol accessible via the electronic portal kp.org. Messages that are handled from 8:00 am to 4:30 pm, Monday through Friday will be included. The study period will run from October 9 to December 11, 2023. Pharmacist Care will not be available for Paxlovid e-visits that need to be reviewed on weekends or holidays. These are managed by virtualist physicians in the regional call center and will be excluded from this study.

Of KPNC's 15 service areas, 4 have not implemented pharmacist management in any facility. These service areas and their facilities are eligible for this study; others must be excluded. The eligible service areas are SCL, SJO, SRF, and SSC. These service areas contain 17 facilities; each facility will be treated as a cluster in the random assignment process.

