#### 4.4.2. Predictors and covariates

The primary predictor is study group, i.e. Pharmacist Care or AFM Pool Care. Covariates are other variables that could potentially mediate, moderate, or confound the association between the primary predictor and the outcomes. In this study, covariates include patient age, sex, race, ethnicity, language spoken, and comorbidities, as well as the patient's neighborhood-level SES.

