The pharmacist and physician surveys have been designed to require no more than 3 to 5 minutes to complete. These surveys will be fielded via Outlook email using a Teams form, as well as on paper via interoffice mail. A small gift to thank pharmacists and physicians for considering participation will be included in the mailing. Responses will be treated as confidential and data will be aggregated, with no individual identifiers associated with data presented in reports.

Data collected from both pharmacists AFMs and will include:

- a. Satisfaction with the process of care (on a 5-point scale)
- b. Suggestions for improving the care process (open-ended)

4.6. Statistical analysis plan.

During the survey and visit review components of this study, it became clear that more patients than projected had received pharmacist care. A preliminary analysis conducted on 12/18/2024, prior to evaluating any outcomes, found that the facility assigned to each e-visit usually did \*not\* match the home facility of the patient who initiated the e-visit. This was most likely due to an operational workflow (which is still being elucidated) that was unanticipated at the time this study was designed and facilities were assigned at random to the Pharmacist Care vs. Physician Care groups. Due to the fact that the patient's "home" facility became imbalanced, we will include this as a covariate in the primary analysis (see below).

The primary analysis will group each patient based on which type of clinician (pharmacist or physician) first accessed the eVisit. This is similar to a per-protocol analysis. A patient whose eVisit was first accessed by a pharmacist will be counted in the pharmacist group, even if the eVisit was referred to a physician. A patient whose eVisit was first accessed by a physician will be included in the physician group, even if the eVisit was referred to a physician group, even if the eVisit was referred to a physician group, even if the eVisit was referred to a pharmacist. We select this approach as the primary analysis because it best reflects what patients experience in real-life care delivery, which this study is intended to evaluate.

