Patient satisfaction and other care experience scores will be compared between the study groups using linear mixed effects regression with log transformation if needed for skewed data, with analyses paralleling that described for the other secondary outcomes.

For all aims, secondary analyses will assess variation in the estimates of treatment effect by age, race/ethnicity/language group, and comorbidity score group (high, medium, low) via stratification by level of the potential effect modifier. These stratified analyses will inform the fitting of regression models with appropriate cross-product terms between the potential effect modifier and study group indicator variable, allowing for a more formal assessment of heterogeneity in treatment effect.

A service area or facility may drop out before completion of the study if they were assigned to AFM Pool Care but add local pharmacist management, thus diverging from their assigned group. Paxlovid e-visits from such a service area or facility will be censored as of the dropout date (the date that local pharmacist management began).

Tests of significance will be two-tailed with an alpha of .05. No Bonferroni or other formal correction for multiple comparisons will be used, but results will be interpreted with the multiple testing issue in mind.

4.8. Sample size and power. To estimate the available sample, we extrapolated from April 2023. This was a month when COVID-19 incidence was low to medium; 4900 e-visits for Paxlovid were made across the 15 KPNC service areas. Based on this, an average of 1089 e-visits occur per week during low to medium COVID-19 incidence periods. However, e-visits that need to be answered on weekend days will not be eligible for pharmacist management; all of these will be excluded from the study. If 5 out of 7 e-visits occur on weekdays, an estimated 778 e-visits occur on weekdays during times of low to medium COVID-19 incidence.

This study will include 17 facilities that serve 872,200 adult members, or 25% of the 3.55 million adult members in the region. Each week, the estimated number of e-visits eligible for study is 25% of 778, or 195. Assuming an 8-week evaluation period, the estimated sample size is 1,560, or 92 patients in each of the 17 clusters.

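### Hours to prescription is analysed without any term for when the e-visit was submitted, although overnight closure enters the outcome directly and the primary grouping does not guarantee balance on submission time

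*Combined protocol and SAP*

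**What the plan says.** **Covariates.** Beyond study group, the pre-specified fixed effects in section 4.6 are neighbourhood deprivation, race/ethnicity and "service area level COVID-19 incidence". In addition, "the patient's home facility and e-visit facility will be handled as random effects". The secondary outcomes take the same approach to covariates. The general list in section 4.4.2 ("covariates include patient age, sex, race, ethnicity, language spoken, and comorbidities", plus neighbourhood SES) has no date, weekday or hour either.

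**The incidence term.** Section 4.6 describes these as the covariates used in the randomisation. Section 4.3 defines that one as "COVID-19 incidence in the service area since the start of the pandemic".

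**Grouping.** The primary analysis will "group each patient based on which type of clinician (pharmacist or physician) first accessed the eVisit". The comparison by assigned group, using the facility on the e-visit worklist, is secondary.

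**Inclusion and outcome.** Section 4.1 takes requests submitted on weekdays and handled between 8:00 am and 4:30 pm, Monday to Friday. Those needing review at weekends or on holidays are excluded. Secondary outcome b in section 4.4.1 counts hours from the request, not from the start of handling, to the prescription order, among patients prescribed Paxlovid.

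**Additional covariates.** Section 4.6 allows exploratory or sensitivity analyses with further covariates, focused on variables that turn out imbalanced by chance. It names none.

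**The concern.** The clock for outcome b starts when the patient submits, but work on the request is confined to office hours. Part of each patient's value is therefore fixed by the hour of submission, before any clinician is involved. If the two first-access groups differ in their share of evening and early-morning requests, their mean hours will differ even when pharmacists and physicians work equally fast.

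In a comparison of concurrent randomised arms within service areas, submission time should be largely balanced. The primary grouping gives no such protection, because patients are classified by who opened the request. The model has nothing to absorb a difference in timing: the incidence covariate does not change during the trial, and facility random effects do not vary with time.

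At stake is the reading of one secondary outcome, faster time to prescription, which the abstract lists among the study's hypotheses. A second cost is precision, which is lost even if the groups are perfectly balanced.

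**Working it through.** **1. Can any planned term track time?** Section 4.1 states: "The eligible service areas are SCL, SJO, SRF, and SSC". A cumulative service-area figure therefore takes at most four values, each constant from October 9 to December 11, 2023. The other fixed effects are patient or neighbourhood characteristics, and the random effects are facilities. None varies with week, weekday or hour.

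**2. The closed interval.** The handling window is 8:00 am to 4:30 pm, or 8.5 h. The gap between consecutive working days is 24 − 8.5 = 15.5 h. I use no longer weekend gap, because requests needing weekend review are excluded. If after-hours requests arrive evenly over the gap (an assumption), the mean wait is 15.5 / 2 = 7.75 h.

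**3. Spurious difference with no true effect.** Difference in mean hours = difference in after-hours share × 7.75 h. The documents give no shares by group, so the differences below are assumed.

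| Assumed difference in after-hours share | Spurious difference in mean hours |
|---|---|
| 5 points | 0.05 × 7.75 = 0.39 h |
| 10 points | 0.10 × 7.75 = 0.78 h |
| 20 points | 0.20 × 7.75 = 1.55 h |

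**4. A yardstick from the plan.** Section 4.8 gives no detectable difference for hours to prescription. For cost (Aim 2) it gives 0.20 SD, which reproduces:

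- Design effect = 1 + (1,560/17 − 1) × 0.01 = 1.908.
- Detectable effect = (1.960 + 0.842) × √(2 × 1.908 / 780) = 0.196 SD.

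For comparison, let s be the share of requests arriving after hours. The queue wait has mean 7.75s and variance s × 15.5²/3 − (7.75s)².

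| Assumed s | SD of queue wait | 10-point difference (0.775 h) in SD units |
|---|---|---|
| 0.20 | 3.69 h | 0.21 |
| 0.40 | 4.74 h | 0.16 |
| 15.5/24 = 0.65 | 5.16 h | 0.15 |

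These SDs cover the queue wait alone. The SD of total hours to prescription would normally be larger, because handling time adds to it, so the standardised figure would be smaller. The 0.20 SD also refers to all e-visits, whereas outcome b is restricted to patients who were prescribed.

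**5. Precision when the groups are balanced.** A single in-hours versus out-of-hours term removes variance s(1 − s) × 7.75² from the queue wait:

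- s = 0.20: 9.61 of 13.61, or 71%.
- s = 0.40: 14.42 of 22.42, or 64%.
- s = 0.65: 13.74 of 26.67, or 52%.

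Hour bands would remove more, since they also separate an early-evening request from one sent just before opening. The gain in total variance cannot be computed, because the documents give no variance for hours to prescription.

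**The case against.** **No route to imbalance is documented.** Section 4.6 does mention an operational workflow that is not yet understood. A reader might infer from this that week, load or hour decided who opened the request first. The text does not say so: the workflow is offered as the likely reason that the facility assigned to an e-visit usually differed from the patient's home facility. Routing is described by group and facility, and both facilities are in the model. This objection stands. The confounding is possible, not shown, and its direction is unknown.

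**The link between volume and COVID-19 is thin.** Section 4.8 says that "an average of 1089 e-visits occur per week during low to medium COVID-19 incidence periods", but only to project the sample. It does not say that volume varied during the trial or affected routing, minutes or counselling. This also stands. The calendar term rests on a weaker basis than the hour term. The one calendar route the plan does describe is censoring, from the dropout date, of sites assigned to physician pools that add local pharmacists.

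**The sensitivity clause could admit submission time.** It could, so it would be wrong to say the plan excludes such an analysis. But the clause names no time variable, is aimed at chance imbalance rather than selection by first access, and leaves the main estimate unadjusted.

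**Charging the full closure overstates the effect.** Multiplying each imbalance by 15.5 h would double the figures in the working. That is a ceiling, reached only if every after-hours request arrived exactly at 4:30 pm. The even-arrival figures are the fair ones to carry.

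**The primary outcome does not need it.** A reader might extend the point to documented counselling and ask for week, weekday and submission terms there. The documents give no mechanism linking submission time to counselling. Nine weeks, five weekdays and two bands would add 8 + 4 + 1 = 13 parameters to a logistic model on about 500 reviewed charts with two facility random effects. That extension is not supported.

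**Conclusion.** The point holds for hours to prescription and is a modest, inexpensive improvement. Two facts can be read directly from the plan: no model term reflects when the e-visit was submitted, and the outcome includes closed hours for requests sent outside the handling window. Because groups are formed by first access, balance on submission time is not assured.

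The size is conditional: about 0.39, 0.78 or 1.55 h for assumed imbalances of 5, 10 or 20 points, with even arrivals over the closure and hours analysed untransformed. The precision argument needs no imbalance at all.

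The documents do not support the stronger conclusion that the first-access comparison is actually confounded by calendar or time of day, or that counselling, minutes and cost are affected. Nor would time terms resolve the wider problem that first access is not randomised. They deal with one identifiable part of it.

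**What to change.** - **Main model for hours to prescription.** Pre-specify submission time as a fixed effect, either within versus outside 8:00 am to 4:30 pm or, preferably, in hour bands. Add calendar period in coarse blocks; three 3-week blocks cover nearly the whole study period with two parameters.
- **Description.** Tabulate the pharmacist share of first access by submission band and by week. This shows directly whether the concern has substance.
- **Clinician minutes, cost and DDI counselling.** Name submission time and calendar block as a sensitivity analysis only, and leave the main models as they are.
- **Status.** State whether the terms were fixed before hours were compared between groups. If not, label the adjusted analysis post hoc.

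The cost is SAP wording and a few model terms. The request timestamp is already needed to compute outcome b, and it precedes any clinician contact, so adjusting for it does not remove part of the effect of who manages the visit. No change to the sample size is needed.
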